10.7. Appendix 7: Pancreatic Monitoring

Glucagon-like peptide 1 agonists have been associated with a possible risk of acute pancreatitis. In 2006, the United States prescribing information for exenatide was revised to include the event of pancreatitis. In 2007, the US prescribing information for this medication was amended to include pancreatitis under "Precautions". Epidemiologic studies have indicated that there is an increased incidence and prevalence of pancreatitis in persons with T2DM.

To enhance understanding of the natural variability of pancreatic enzymes in the T2DM population and, to assess for any potential effects of LY3493269 on the exocrine pancreas, amylase and lipase values will be monitored in all current and future clinical trials with LY3493269.

Additional monitoring will be requested for amylase or lipase values ≥3X the ULN at any visit after randomization. Lipase and amylase may also be obtained at any time during the clinical trials for any participant suspected of having symptoms suggestive of pancreatitis (such as severe GI signs and/or symptoms), at the investigator's discretion.

Acute pancreatitis is an AE defined as an acute inflammatory process of the pancreas that may also involve peripancreatic tissues and/or remote organ systems. The diagnosis of acute pancreatitis requires 2 of the following 3 features:

- abdominal pain characteristic of acute pancreatitis
- serum amylase and/or lipase $>3 \times ULN$, and
- characteristic findings of acute pancreatitis on CT scan or magnetic resonance imaging

Most participants with acute pancreatitis experience abdominal pain that is located generally in the epigastrium and radiates to the back in approximately one-half of the cases. The pain is often associated with nausea and vomiting.

Participants diagnosed with pancreatitis will be discontinued from the study. Investigators will be responsible for following, through an appropriate health care option, these pancreatitis AEs until the events resolve or are explained. Adverse events that meet the diagnostic criteria of acute pancreatitis will be captured as SAEs. For all other pancreatic AEs (such as idiopathic or asymptomatic pancreatic enzyme abnormalities), the investigator will be responsible for determining the seriousness of the event (AE or SAE) and the relatedness of the event to IP.

10.8. Appendix 8: Hypersensitivity Event Tests

This table lists the recommended tests that should be obtained in case of a clinically significant hypersensitivity/allergy event. Selected tests may be obtained in the event of anaphylaxis or generalized urticaria.

Anti-LY antibodies (immunogenicity)	Tryptase
LY concentration (PK)	N-methylhistamine
	Drug-specific IgE ^a
	Basophil activation test ^a
	Complements
	Cytokine Panel

Abbreviations: Ig = immunoglobulin; LY = LY3493269; PK = pharmacokinetics.

^a Basophil activation test will be performed if a drug-specific IgE assay is unavailable.

10.9. Appendix 9: Abbreviations

Term	Definition
ADA	antidrug antibody
AE	adverse event: Any untoward medical occurrence in a patient or clinical investigation participant administered a pharmaceutical product that does not necessarily have a causal relationship with this treatment. An AE can therefore be any unfavorable and unintended sign (including an abnormal laboratory finding), symptom, or disease temporally associated with the use of a medicinal (investigational) product, whether or not related to the medicinal (investigational) product.
ALP	alkaline phosphatase
ALT	alanine aminotransferase
AST	aspartate aminotransferase
AUC	area under the concentration versus time curve
BG	blood glucose
ВР	blood pressure
CI	confidence interval
C _{max}	maximum observed drug concentration
complaint	A complaint is any written, electronic, or oral communication that alleges deficiencies related to the identity, quality, purity, durability, reliability, safety or effectiveness, or performance of a drug or drug delivery system.
compliance	Adherence to all study-related, good clinical practice (GCP), and applicable regulatory requirements.
СР	clinical pharmacologist
CRF	case report form
CRP	clinical research physician: Individual responsible for the medical conduct of the study. Responsibilities of the CRP may be performed by a physician, clinical research scientist, global safety physician, or other medical officer.
CRU	clinical research unit
СТ	computed tomography
CV	cardiovascular
ECG	electrocardiogram
eCRF	electronic case report form

CONFIDENTIAL

enroll The act of assigning a participant to a treatment. Participants who are enrolled in the

study are those who have been assigned to a treatment.

enter Participants entered into a study are those who sign the informed consent form directly

or through their legally acceptable representatives.

GCP good clinical practice

GI gastrointestinal

GIP glucose-dependent insulinotropic polypeptide

GLP-1 glucagon-like peptide-1

GLP-1 receptor

GLP-1RA GLP-1 receptor agonist

HIV human immunodeficiency virus

HR heart rate

IB Investigator's Brochure

ICF informed consent form

ICH International Council for Harmonisation

IEC independent ethics committee

informed consent A process by which a participant voluntarily confirms his or her willingness to

participate in a particular study, after having been informed of all aspects of the study that are relevant to the participant's decision to participate. Informed consent is documented by means of a written, signed, and dated informed consent form.

INR International normalized ratio

interim analysis An interim analysis is an analysis of clinical study data, separated into treatment groups,

that is conducted before the final reporting database is created/locked.

investigator A person responsible for the conduct of the clinical study at a study site. If a study is

conducted by a team of individuals at a study site, the investigator is the responsible

leader of the team and may be called the principal investigator.

IP investigational product

IRB institutional review board

NASH nonalcoholic steatohepatitis

participant Equivalent to CDISC term "subject": an individual who participates in a clinical trial,

either as recipient of an investigational medicinal product or as a control

PG plasma glucose

CONFIDENTIAL

PK/PD pharmacokinetics/pharmacodynamics

PR pulse rate

randomize The process of assigning participants to an experimental group on a random basis.

QT interval corrected using Fridericia's formula

SAD single-ascending dose

SAE serious adverse event

SAP statistical analysis plan

SC subcutaneous

screen The act of determining if an individual meets minimum requirements to become part of

a pool of potential candidates for participation in a clinical study.

SNAC salcaprozate sodium

SoA Schedule of Activities

SRP Safety Review Panel

T2DM type 2 diabetes mellitus

TBL total bilirubin level

TE-ADA treatment-emergent-antidrug antibody

TEAE treatment-emergent adverse event: An untoward medical occurrence that emerges

during a defined treatment period, having been absent pretreatment, or worsens relative to the pretreatment state, and does not necessarily have to have a causal relationship

with this treatment.

time of maximum observed drug concentration

ULN upper limit of normal

VAS visual analog scale

11. References

2. ABBREVIATIONS

Abbreviations pertain to the Statistical Analysis Plan (SAP) only (not the tables, figures and listings [TFLs]).

| | |
|------------------|--|
| ADA | Anti-drug antibody |
| AE | Adverse event |
| ALP | Alkaline phosphatase |
| ALT | Alanine aminotransferase |
| AUC | Area under the concentration versus time curve |
| AST | Aspartate aminotransferase |
| BW | Body weight |
| CI | Confidence interval |
| C _{max} | Maximum observed drug concentration |
| CRF | Case Report Form |
| CRU | Clinical Research Unit |
| CSR | Clinical Study Report |
| ECG | Electrocardiogram |
| HR | Heart rate |
| ICH | International Conference on Harmonisation |
| LS | Least squares |
| MedDRA | Medical Dictionary for Regulatory Activities |
| PD | Pharmacodynamic |
| PG | Plasma glucose |
| PK | Pharmacokinetic |
| QD | Once daily |
| QTcF | QT interval corrected using Fridericia's formula |
| SAE | Serious adverse event |
| SAP | Statistical Analysis Plan |
| SNAC | Salcaprozate sodium |
| TBL | Total bilirubin |
| TE ADA | Treatment-emergent anti-drug antibody |
| TEAE | Treatment-emergent adverse event |
| TFLs | Tables, Figures, and Listings |

| | |
|-----------|---|
| t_{max} | Time of maximum observed drug concentration |
| ULN | Upper limit of normal |
| VAS | Visual analog scale |
| WHO | World Health Organization |

3. INTRODUCTION

This SAP has been developed after review of the Clinical Study Protocol (final version dated 11 September 2020), Protocol Amendment (a) (final version dated 05 March 2021) SAP Version 1 (final version dated 04 November 2020), and SAP Version 2 (final version dated 08 March 2021).

This SAP describes the planned analysis of the safety, tolerability, pharmacokinetic (PK) and pharmacodynamic (PD) data from this study. A detailed description of the planned TFLs to be presented in the clinical study report (CSR) is provided in the accompanying TFL shell document.

The intent of this document is to provide guidance for the statistical and PK analyses of data. In general, the analyses are based on information from the protocol, unless they have been modified by agreement with Eli Lilly and Company. A limited amount of information concerning this study (e.g., objectives, study design) is given to help the reader's interpretation. When the SAP and TFL shells are agreed upon and finalized, they will serve as the template for this study's CSR.

This SAP supersedes the statistical considerations identified in the protocol; where considerations are substantially different, they will be so identified. If additional analyses are required to supplement the planned analyses described in this SAP, they may be performed and will be identified in the CSR. Any substantial deviations from this SAP will be agreed upon with Eli Lilly and Company and identified in the CSR. Any minor deviations from the TFLs may not be documented in the CSR.

This SAP is written with consideration of the recommendations outlined in the International Conference on Harmonisation (ICH) E9 Guideline entitled Guidance for Industry: Statistical Principles for Clinical Trials¹ and the ICH E3 Guideline entitled Guidance for Industry: Structure and Content of Clinical Study Reports².

4. STUDY OBJECTIVES

4.1 Primary Objective

The primary objective of the study is to investigate the safety and tolerability of LY3493269 following 3 consecutive once daily (QD) oral doses in healthy participants.

The primary endpoint of the study is treatment-emergent adverse events (TEAEs).

4.2 Secondary Objective

The secondary objective of the study is to characterize the PK of LY3493269 following 3 consecutive QD oral doses in healthy participants.

The secondary endpoints of the study are:

- Area under the concentration versus time curve (AUC)

- Maximum observed drug concentration (C_{max}).

4.3 Exploratory Objectives

The exploratory objectives of the study are:

- To investigate the PD effects of LY3493269 following 3 consecutive QD oral doses in healthy participants
 - Endpoint: Changes from baseline levels of fasting glucose, insulin, C-peptide, triglycerides, and body weight (BW)
- To assess PK of salcaprozate sodium (SNAC) following oral administration in healthy participants
 - Endpoint: AUC and C_{max}
- To explore the effect of LY3493269 on appetite and food intake following 3 consecutive QD oral doses in healthy participants
 - Endpoint: Change in visual analog scale (VAS) score for appetite assessment in a fasted state
- To characterize immunogenicity of LY3493269 following 3 QD oral doses in healthy participants
 - Endpoint: Incidence of treatment-emergent anti-drug antibody (TE ADA)
- To assess the product palatability of LY3493269 tablets.
 - Endpoint: Responses to tablet palatability questionnaire.

5. STUDY DESIGN

Study GZHF is a Phase 1, single-center, randomized, placebo-controlled, multiple dose, dose escalation study in 4 planned cohorts of up to 14 healthy participants randomly assigned in each cohort.

This study will evaluate the safety, tolerability, and PK of 3 consecutive QD oral doses of LY3493269. In addition, the PD effects of LY3493269 on fasting glucose, insulin, triglycerides, and appetite will be explored following the 3 consecutive oral QD doses of LY3493269.

In each cohort, up to 14 participants may be randomly assigned to achieve 10 completers with 8 participants receiving LY3493269 and 2 participants assigned to receive placebo. Participants who are randomly assigned but not administered treatment prior to discontinuation may be replaced to ensure that the target number of participants complete the study.

This is an investigator- and participant-blind study; the sponsor is not blinded.

Study randomization shall occur after confirmation of eligibility.

The planned LY3493269 oral doses for this study range from 8 to 48 mg, administered in the 4 planned “dose cohorts”:

- Cohort 1: 8 mg LY3493269 (with 600 mg SNAC)
- Cohort 2: 24 mg LY3493269 (with 600 mg SNAC)

- Cohort 3: 48 mg LY3493269 (with 600 mg SNAC)
- Cohort 4: 24 mg LY3493269 (with 300 mg SNAC)

[figure not shown]
Cohorts 1 to 3 evaluate doses of LY3493269 from 8 to 48 mg, each dose in combination with 600 mg SNAC. Cohort 4 evaluates a 24-mg dose of LY3493269 with half the amount (300 mg) of SNAC.

The LY3493269 dose levels may be adjusted (for example, dose increments may be reduced, a dose level may be repeated, or a lower/intermediate dose may be administered) based on ongoing review of available safety, tolerability, PK, and PD data. Any proposal to adjust doses from those planned and stated in the protocol, together with supporting data, will be reviewed by an independent safety review panel.

Participants will undergo safety (including but not limited to adverse events [AEs], medical assessments, clinical laboratory tests, BW, vital signs, and electrocardiograms [ECGs]), PK, and PD assessments.

Safety data including, but not limited to AEs, clinical laboratory tests, vital signs, ECGs, BW, hypoglycemic events, and VAS assessments up to Day 8 from at least 8 participants who have received study intervention will be reviewed jointly by the principal investigator and sponsor before a joint decision is made to escalate to the next planned dose level.

A general schema for GZHF can be seen in **Figure 1**.

Abbreviations: SNAC = salcaprozate sodium; LY = LY3493269; PL = placebo.

Figure 1 - General schema for GZHF

7. SAMPLE SIZE JUSTIFICATION

The sample size is customary for Phase 1 studies evaluating safety and PK and is not powered on the basis of statistical hypothesis testing.

Up to approximately 56 participants may be randomly assigned to study intervention to ensure approximately 10 evaluable participants (8 receiving LY3493269 and 2 receiving placebo) from

each of the 4 cohorts complete the study. Participants who are randomized but not administered treatment prior to discontinuation may be replaced to ensure that the target number of participants complete the study.

Participants who discontinue early may be replaced after consultation with the investigator and sponsor. The replacement participant will be assigned to the same treatment as the discontinued participant.

8. DEFINITION OF ANALYSIS POPULATIONS

The “Entered” population will consist of all participants who sign the informed consent form.

The “Enrolled” population will consist of all participants assigned to treatment, regardless of whether they take any doses of study treatment, or if they took the correct treatment. Participants will be analyzed according to the treatment group to which they were assigned.

The “Safety” population will consist of all participants randomly assigned to study intervention and who take at least 1 dose of study intervention. Participants will be analyzed according to the intervention they actually received.

The “Pharmacokinetic” population will consist of all participants who received at least 1 full dose of LY3493269 and have evaluable PK data. Participants may be excluded from the PK summary statistics and statistical analysis if a participant has an AE of vomiting that occurs at or before 2 times median time of maximum observed drug concentration (t_{max}).

The “Pharmacodynamic” population will consist of all participants who received at least 1 dose of LY3493269 and have evaluable PD data. Participants may be excluded from the PD summary statistics and statistical analysis if a participant has an AE of vomiting that occurs at or before 2 times median t_{max} .

All protocol deviations that occur during the study will be considered for their severity/impact and will be taken into consideration when participants are assigned to analysis populations.

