2.2.1. Summary of Clinical Experience

Study J1X-MC-GZHA

Study J1X-MC-GZHA (GZHA) was a first-in-human, randomized, placebo-controlled, SAD study investigating the safety, tolerability, and PK of LY3493269 administered as single SC doses in healthy participants. In addition, a cohort of 6 healthy participants was planned to receive a single intravenous dose of LY3493269, to allow estimation of the absolute SC bioavailability of LY3493269.

As of 06 April 2020, 3 cohorts of 6 participants received SC doses of LY3493269 at each of the 0.15-, 0.5-, and 1.5-mg dose levels. There was an increase in the number of AEs (such as nausea, vomiting, and abdominal distension) related to the study drug with increasing doses of LY3493269 as compared to placebo. The dose of 1.5 mg was considered not well tolerated due to increases in the number of GI events, some requiring treatment. However, the prespecified dose escalation stopping criteria were not met. Due to concerns about safety and tolerability with the next planned SC dose of 3 mg, the sponsor decided to stop further dosing.

No deaths, serious adverse events (SAEs), or discontinuations due to AEs were noted in this study up to the data cut-off, 06 April 2020.

Of the 30 healthy participants who received either LY3493269 or placebo, 26 (86.7%) reported at least 1 TEAE.

Consistent with the incretin class, GI events such as abdominal distension, nausea, vomiting, and diarrhea were the most commonly reported AEs in Study GZHA. In addition, decreased appetite was also one of the most frequently reported AEs. All TEAEs were considered as mild in severity by the investigator, even though some required treatment. In Cohort 2, where subjects received 0.5 mg, 1 subject out of 6 presented with nausea, and none presented with vomiting. However, 3 subjects out of 6 in Cohort 3 receiving 1.5 mg reported GI AEs of nausea and vomiting, requiring anti-emetics. Several other GI AEs were reported in Cohort 3 (for example, abdominal pain upper, constipation, eructation, epigastric discomfort, dry mouth, and dyspepsia) not previously reported in the other cohorts.

No clinically significant changes in laboratory data, injection-site reactions, or severe hypoglycemia events were noted.

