4.1. Overall Design

Study GZHF is a Phase 1, single-center, randomized, placebo-controlled, multiple dose, dose-escalation study in 4 planned cohorts of up to 14 healthy participants randomly assigned in each cohort.

This study will evaluate the safety, tolerability, and PK of 3 consecutive once-daily oral doses of LY3493269. In addition, the PD effects of LY3493269 on fasting glucose, insulin, triglycerides, and appetite will be explored following the 3 consecutive oral once-daily doses of LY3493269.

In each cohort, up to 14 participants may be randomly assigned to achieve 10 completers with 8 participants receiving LY3493269 and 2 participants assigned to receive placebo. Participants who are randomly assigned but not administered treatment prior to discontinuation may be replaced to ensure that the target number of participants complete the study.

This is an investigator- and participant-blind study; the sponsor is not blinded.

Study randomization shall occur after confirmation of eligibility.

The planned LY3493269 oral doses for this study range from 8 to 48 mg (Section 1.2), administered in the 4 planned "dose cohorts":

- Cohort 1: 8 mg LY3493269 (with 600 mg SNAC)
- Cohort 2: 24 mg LY3493269 (with 600 mg SNAC)
- Cohort 3: 48 mg LY3493269 (with 600 mg SNAC)
- Cohort 4: 24 mg LY3493269 (with 300 mg SNAC)

Cohorts 1 to 3 evaluate doses of LY3493269 from 8 to 48 mg, each dose in combination with 600 mg SNAC. Cohort 4 evaluates a 24-mg dose of LY3493269 with half the amount (300 mg) of SNAC. PK exposures from 24 mg LY3493269 administered with half the amount of SNAC (i.e. 300 mg SNAC in Cohort 4) are anticipated to be comparable to exposures from the 24-mg dose in Cohort 2, and not exceed exposures from the 48-mg dose in Cohort 3. Hence, Cohort 4 may be initiated at the same time as Cohort 3 if safety and tolerability data from Cohort 2 do not preclude dosing of 24 mg LY3493269 or higher doses.

The LY3493269 dose levels may be adjusted (for example, dose increments may be reduced, a dose level may be repeated, or a lower/intermediate dose may be administered) based on ongoing review of available safety, tolerability, PK, and PD data (Section 6.6). Any proposal to adjust doses from those planned and stated in the protocol, together with supporting data, will be reviewed by an independent SRP.

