9.3. Populations for Analyses

The following populations are defined:

Population	Description		
Entered	All participants who sign the ICF		
Enrolled	All participants assigned to treatment, regardless of whether they take any doses of study treatment, or if they took the correct treatment. Participants will be analyzed according to the treatment group to which they were assigned.		
Safety	All participants randomly assigned to study intervention and who take at least 1 dose of study intervention. Participants will be analyzed according to the intervention they actually received.		
Pharmacokinetic Analysis	All participants who received at least 1 full dose of LY3493269 and have evaluable PK sample.		
Pharmacodynamic Analysis	All participants who received at least 1 dose of LY3493269 and have evaluable PD data.		

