10. INTERIM ANALYSES

Interim access to safety and tolerability (and any available PK or PD) data is scheduled to occur after every dosing session. The investigator will remain blinded, and the Lilly sponsor team will be unblinded during these reviews.

No interim statistical analyses are planned.

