11. CHANGES FROM THE PROTOCOL SPECIFIED STATISTICAL ANALYSES

There were no changes from the protocol specified statistical analyses.

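### The SAP's vomiting exclusion is optional and participant-wide: it can discard a valid Day 1 PK profile and shift the dose-proportionality ratio, and no analysis without exclusions is required

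*SAP*

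**What the plan says.** SAP Section 8 takes the PK population as everyone with at least one full dose of LY3493269 and evaluable PK data, then adds: "Participants may be excluded from the PK summary statistics and statistical analysis if a participant has an AE of vomiting". A time limit follows, so the clause reaches only an event "that occurs at or before 2 times median time of maximum observed drug concentration". A parallel sentence covers pharmacodynamics: "Participants may be excluded from the PD summary statistics and statistical analysis if a participant has an AE of vomiting", with the same window.

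The section does not say when *may* applies, which of the three doses starts the window, whose median tmax is used, who decides, or when. It asks for no analysis without the exclusions.

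The protocol's PK population (Section 9.3) has no vomiting clause: "All participants who received at least 1 full dose of LY3493269 and have evaluable PK sample". SAP Section 11 nevertheless states: "There were no changes from the protocol specified statistical analyses".

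SAP Section 9.3.2 analyses Day 1 and Day 3 independently and judges dose proportionality by the dose-normalized geometric mean ratio between the highest and lowest doses. SAP Section 9.6.6 predicts ECG changes at each treatment's observed geometric mean Cmax.

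**The concern.** Cmax and AUC are the secondary endpoints, with a target of 8 active participants per cohort, so one exclusion removes 1/8 = 12.5% of a cohort's active data. Four features of the rule matter.

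- **Scope.** Days 1 and 3 are separate analyses, but the exclusion attaches to the participant. Vomiting after dose 2 or 3 cannot alter absorption already observed on Day 1, yet the wording lets that profile be dropped.
- **Discretion.** Two analysts could follow the same sentence and report different results.
- **Timing.** A cutoff built on this study's median tmax is known only once concentrations exist. The sponsor derives the PK parameters (SAP Section 9.3.1) and sees any available PK at the data reviews (SAP Section 10).
- **Possible clustering by dose.** In the subcutaneous study GZHA, no participant vomited at 0.5 mg, whereas "3 subjects out of 6 in Cohort 3 receiving 1.5 mg reported GI AEs of nausea and vomiting" (Protocol Section 2.2.1). If the oral formulation behaves similarly, exclusions fall mainly at the higher doses.

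What could move is the Cmax and AUC summaries, the highest-to-lowest ratio and, if it comes from the same population, the geometric mean Cmax used in the ECG predictions.

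**Working it through.** **Inputs from the documents.** There are 4 cohorts of up to 14 (4 × 14 = 56, the stated maximum), with a target of 8 active completers each (4 × 8 = 32). Doses follow Protocol Section 4.1 and SAP Section 5: 8, 24 and 48 mg with 600 mg SNAC, and 24 mg with 300 mg SNAC. The treatment table in SAP Section 6 lists other doses for Cohorts 3 and 4. That needs reconciling separately, and the figures below apply only to the doses used here. The documents give no figure for the effect of the exclusion, so there is none to reproduce.

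**Assumptions.** Protocol Section 4.2 calls variability in oral bioavailability exceptionally high but gives no value. Geometric CVs of 40%, 80% and 120% are assumed, so the log-scale SD is s = √ln(1 + CV²) = 0.385, 0.703 and 0.944. Vomiting rates, their link to exposure and the drug lost are also assumed.

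**Model.** The SAP power model was simulated: log PK on log-dose plus a SNAC indicator, with true slope 1. The true 48/8 dose-normalized ratio is then 1.00, and the estimate is exp[(slope − 1) × ln(48/8)].

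**Step 1: precision with all 32 kept.** The 90% CI half-width is t(0.95; 29 df) × s × √V × ln 6, where V is the log-dose element of (X′X)⁻¹. As a factor this is 1.38, 1.81 and 2.22 for the three CVs.

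**Step 2: drop 1, 2 or 3 of the 8 participants at 48 mg.**

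| CV | 48/8 ratio, highest exposures dropped | 48/8 ratio, lowest exposures dropped | 48 mg geometric mean relative to truth, highest dropped |
|---|---|---|---|
| 40% | 0.94 / 0.88 / 0.85 | 1.08 / 1.13 / 1.18 | 0.93 / 0.86 / 0.81 |
| 80% | 0.88 / 0.80 / 0.73 | 1.13 / 1.26 / 1.35 | 0.86 / 0.77 / 0.68 |
| 120% | 0.85 / 0.75 / 0.66 | 1.19 / 1.36 / 1.50 | 0.83 / 0.70 / 0.59 |

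The sign depends on who is dropped. In the ECG prediction, the term slope × Cmax scales with the last column, if the Cmax used there carries the exclusions.

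**Step 3: vomiting driven by exposure.** The probability of vomiting is logistic in log exposure (assumed slope 2), set to 25% or 50% at the typical 48 mg exposure. Ranges run across the three CVs.

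| Policy | 25% vomiting | 50% vomiting |
|---|---|---|
| Exclude all vomiters | 0.72-0.94 | 0.65-0.90 |
| Keep all, no drug lost | 0.99-1.00 | 0.99-1.01 |
| Keep all, vomiters retain 70% of exposure | 0.90-0.91 | 0.85-0.86 |
| Keep all, vomiters retain 50% of exposure | 0.81-0.85 | 0.73-0.75 |

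Neither policy is always closer to 1.00. With CV 40%, 50% vomiting and half the exposure retained, excluding gives 0.90 and keeping gives 0.73. With CV 80%, 50% vomiting and 70% retained, excluding gives 0.75 and keeping gives 0.86.

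Every shift in Steps 2 and 3 is smaller than the matching half-width in Step 1. On the low side those limits are 1/1.38 = 0.72, 1/1.81 = 0.55 and 1/2.22 = 0.45. Unlike sampling error, though, the shift is systematic.

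**Step 4: does vomiting on one day spoil another day's profile?** Protocol Section 2.2.1 gives a half-life in days (value redacted), and Section 4.2 expects no steady state after three doses. Assume a half-life of T = 3 to 7 days and near-immediate absorption, and let r = 2^(−1/T). Doses 1, 2 and 3 then contribute to Day 3 AUC(0-24) in proportion r² : r : 1.

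- T = 3: r = 0.794, r² = 0.630, sum 2.424. Losing dose 1 costs 0.630/2.424 = 26%; losing dose 2 costs 0.794/2.424 = 33%.
- T = 7: r = 0.906, r² = 0.820, sum 2.726. The losses are 0.820/2.726 = 30% and 0.906/2.726 = 33%.

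A fully lost earlier dose therefore removes about 26-33% of Day 3 AUC(0-24). Contamination runs forward in time and never back to Day 1.

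**The case against.** The strongest defence is that the rule is pharmacologically sound. It is confined to early vomiting, when an oral dose may be lost, and Step 3 shows that keeping such participants can bias the ratio by as much as excluding them. Step 4 adds that removing a Day 3 profile after Day 1 or Day 2 vomiting is defensible. All of this stands. It rules out both keeping everyone as the sole analysis and setting aside only the day on which vomiting occurred. It does not justify deleting Day 1 for a later event.

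The evidence that vomiting rises with dose is limited: single subcutaneous doses, 6 per group, no time window. The oral study GZHB used the same 8, 24 and 48 mg doses with a different enhancer. Its most frequent events are listed as decreased appetite, nausea and abdominal distension, not vomiting (Protocol Section 2.2.1). Clustering at high doses is therefore possible but not shown.

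A reader might infer that sponsor unblinding opens a treatment comparison to manipulation, since Protocol Section 4.1 says: "This is an investigator- and participant-blind study; the sponsor is not blinded". The documents do not support that for PK. The PK population holds only LY3493269 recipients, analysis of placebo samples is not planned (Protocol Section 8.5.1), the planned dose is set by cohort, and SAP Section 8 names no decision-maker. What remains is narrower: the choice can be made with concentrations in view.

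The vomiting clause can also be read as spelling out the protocol's word *evaluable*, with technical detail left to the SAP (Protocol Section 9.4). That makes the silence in SAP Section 11 a disclosure gap more than a contradiction.

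Finally, excluded participants stay highlighted in the listings (SAP Section 9.1), and dose proportionality is exploratory in an unpowered study. Exclusions will be visible, but the summaries and models would still appear in only one form.

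**Conclusion.** The concern holds as a fault in how the rule is written, and it should be corrected. The rule is optional, covers the whole participant, depends on a cutoff known only after assay, and has no companion analysis. Loss of a valid Day 1 profile follows from the wording alone and needs no assumption.

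A reader might go further and conclude that the rule understates high-dose exposure. The documents do not support a fixed direction. Dropping high-exposure vomiters lowers the ratio, dropping low-exposure vomiters raises it, and keeping participants who lost drug lowers it. When vomiting is exposure-driven and all vomiters are excluded, the 48/8 ratio is 0.72-0.94 at 25% vomiting and 0.65-0.90 at 50%, against a true 1.00. These figures rest on assumed CVs, vomiting rates, logistic slope and drug loss. They lie inside the 90% CI half-width of a factor of 1.38-2.22, so they show what the wording could allow and are not a forecast for this study.

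**What to change.** 1. Replace *may* with a fixed rule that runs from the affected dose forward. Day 1 vomiting inside the window flags the Day 1 and Day 3 profiles. Day 2 or Day 3 vomiting flags Day 3 only. Day 1 profiles collected before the event stay in.
2. State the tmax reference that sets the window. Vomiting onset and end times are already recorded for each event (Protocol Section 8.2.5.3), so the flagged list then follows mechanically. If the reference is set in advance, the list can be fixed before concentrations are released; a median from this study's own data would not allow that.
3. Report the Cmax and AUC summaries and the power model twice: with all evaluable dosed participants, and with flagged profiles removed. Say which version supplies the geometric mean Cmax for the ECG predictions.
4. Declare the rule, with its reason, in SAP Section 11, and make the parallel PD sentence equally definite.

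The cost is SAP wording and one extra set of PK tables. The downside is that the all-participant version includes some profiles with lost drug. Neither version alone is unbiased, so the two should be read together.
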